## **1. Introduction**

Dry eye disease (DED) is a chronic multifactorial disease of the ocular surface characterized by a loss of homeostasis of the tear film, which is accompanied by ocular symptoms caused by hyperosmolarity, ocular surface inflammation and neurosensory abnormalities [1,2]. DED prevalence varies according to the definition used and the characteristics of the population studied, but it ranges from 5% to 50%, is more frequent in women and increases with age [3]. Currently, evidence suggests that all forms of DED have an evaporative component because without evaporation, hyperosmolarity cannot occur [4].

Meibomian gland dysfunction (MGD) is the most common etiology of tear film evaporation, and it is characterized by the obstruction of meibomian glands due to terminal duct obstruction and/or changes in meibum quality and quantity [4,5]. The management and therapy subcommittee of the TFOS DEWS II recommended intense pulsed light (IPL) as a second step therapy for MGD when education, lid hygiene, warm compresses and ocular lubrications do not achieve the desired effect [6]. IPL is a form of light therapy that uses flash lamps to emit noncoherent, polychromatic high-intensity light of determined wavelength spectrum, ranging from 500 to 1200 nm [7]. Using these wavelengths, the potentially harmful ultraviolet radiation, which occurs below 500 nm, is filtered [8]. In 2002, Toyos et al. reported that patients with dry eye disease (DED) who received IPL treatment for rosacea, acne or other skin disorders reported improvements in their dry eye symptoms [9]. This finding led to the development of different IPL devices to specifically treat DED. Currently, different studies have shown that IPL is a safe and effective treatment that improves the signs and symptoms of patients with DED owing to MGD [9–15]. The main mechanism of action of IPL is thermal. IPL energy absorbed by hemoglobin which causes thrombosis of abnormal blood vessels reduces the concentration of inflammatory mediators in the eyelid and meibomian glands, thus preventing their dysfunction and improving meibum flow [16].

Combined or additional therapies in MGD treatment have emerged such as Microblepharoexfoliation (MBE). MBE is a novel in-office treatment that works by exfoliating the eyelid margins to remove the accumulated biofilm debris, epithelial keratinization and capped meibomian glands, resulting in better meibum outflow. Different studies have shown that MBE improves DED symptoms [17,18], demodex blepharitis [17–20] and meibomian gland function [18,19,21]. In addition, meta-analyses recommend combining IPL with meibomian gland expression (MGX) compared to IPL or MGX alone [22–24].

However, to the best of our knowledge, we have not found any studies evaluating the benefits of MBE combined with IPL and MGX.

Consequently, the purpose of the current study is to evaluate whether MBE combined with IPL and MGX leads to an improvement of symptoms and signs in patients with DED due to MGD.

## **2. Methods**

This prospective, unmasked, non-randomized and controlled study was approved by the clinical research ethics committee of the University of Murcia (ID: 4097/2022), adhered to the tenets of the Declaration of Helsinki, and was performed at the Novovision Ophthalmology Clinic from April 2022 to January 2023. Informed consent was obtained from each patient before enrollment in the study.

### **2.1 Subjects**

Patients with DED due to MGD attending Novovision Ophthalmology Clinic were enrolled. The inclusion criteria were as follows: (1) age  $\geq$  18 years old; (2) DED diagnosis according to DEWS II [25] meeting one of the following conditions: (2.1) ocular surface disease index (OSDI) score  $\geq$  13; (2.2) NIBUT  $<$  10 seconds; and (2.3) ocular surface staining with  $>$  5 or 9 corneal or conjunctival stains, respectively, and (3) MGD diagnosis according to the international workshop on MGD [26] meeting two of the following conditions: (3.1) irregularity of the eyelid margin or mucocutaneous junction; (3.2) vascularity of the eyelid margin; (3.3) plugged or capped Meibomian gland orifices; (3.4) Meibomian gland atrophy; or (3.5) decreased meibum quality and quantity. The exclusion criteria included: (1) skin pathologies that prevent IPL treatment; (2) all corneal disorders that affect diagnostic tests, such as: (2.1) active corneal infections; and (2.2) corneal dystrophies; (3) active ocular allergy; (4) pregnant or lactating women; and (5) patients who did not understand or comprehend the informed consent. Systemic or ocular diseases, previous systemic or ocular treatments and ocular surgeries with more than 6 months of postoperative evolution were not considered exclusion criteria to better reflect the patient population. Contact lens users were instructed not to wear their contact lenses one week before baseline and follow-up examinations.

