### **2.3 Clinical assessment**

Parameters were assessed with the S390L Firefly WDR slit lamp (Shangai Mediworks Precision Instruments Co. Shangai, China) that includes a dry eye module designed to perform objective and non-invasive measures, which are analyzed by an artificial intelligence (AI) identification system (Mediview R3.0 software). To assess treatment efficacy, parameters were measured at baseline and the last visit. DED symptoms were assessed with the ocular surface disease index (OSDI) and symptom assessment in dry eye (SANDE) questionnaires. Ocular surface measurement was carried out by one examiner ([name]) in the following sequence to best preserve the integrity of the tear film to avoid affecting the test results: (1) tear film stability and volume; (2) ocular hyperemia; (3) ocular surface staining (OSS) and (4) meibomian gland analysis. Except for OSDI and SANDE questionnaires, which were collected per subject, all other clinical outcomes were collected per eye. To evaluate treatment safety, post-treatment adverse events were reported.

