## **2.6 Statistical analysis**

Statistical analyses were performed with SPSS statistics software, version 26.0 (IBM Corporation, Armonk, NY, USA). The sample size was estimated using the GRANMO calculator, version 7.12 (Municipal Institute of Medical Research, Barcelona, Spain). It was calculated on the basis of assumed mean differences in F-NIBUT and MGYSS between the treatment and control groups at 2 months after the treatment onset, with values of  $3.04 \pm 3.86$  and  $19.75 \pm 5.45$ , respectively. These assumed differences were based on the findings of a pilot study with 16 eyes of 8 patients in each group. With these assumptions, a sample size of 26 eyes per group would yield a power > 80% and a statistically significant paired difference of 95% confidence. Continuous variables were displayed as the mean  $\pm$  standard deviation (SD) with interquartile ranges [IQRs], while ordinal categorical variables were expressed as frequencies (n) and percentages (%). After testing for normality and homogeneity of variance, the paired Student's *t*-test (parametric) or Wilcoxon's signed-rank test (nonparametric) was performed to compare intra-group clinical

outcomes. Within each group, the increment ( $\Delta$ ) was calculated. It was defined as the change from the last visit (LV) to baseline (B) " $\Delta = LV - B$ ". Inter-group clinical outcomes, were analyzed with the unpaired Student's *t*-test (parametric) or Mann-Whitney's U test (nonparametric). Between each group, the differences were calculated as " $\Delta_{Treatment\ group} - \Delta_{Control\ group}$ ". The Pearson's (parametric) or Spearman's Rho correlation coefficient (nonparametric) was used to analyze the correlations between the variables. Stepwise multiple linear regression analysis was performed to detect the influential factors in dry eye symptoms ( $\Delta$ OSDI and  $\Delta$ SANDE). In addition, One-Way ANOVA (parametric) was performed to determine if there were statistically significant differences in  $\Delta$ MGYSS according to baseline L-MGD-grade. A post hoc analysis by Bonferroni's test was carried out to determine statistically significant differences between baseline L-MGD grade. The level of significance was  $P < 0.05$  for all of the comparisons.

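### The written DED entry rule needs only one of three items, so it admits patients with OSDI below 13, and patients with neither short NIBUT nor qualifying staining, against the document's own description of DED

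*Combined protocol and SAP*

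**What the plan says.** Section 2.1 has two cumulative diagnostic criteria. Criterion 2 is "DED diagnosis according to DEWS II [25] meeting one of the following conditions: (2.1) ocular surface disease index (OSDI) score" of at least 13 (item 2.1), NIBUT below 10 s (2.2), "and (2.3) ocular surface staining with" more than 5 corneal or 9 conjunctival stains (2.3). Criterion 3 is a "MGD diagnosis according to the international workshop on MGD [26] meeting two of the following conditions", followed by five lid or gland findings, the last joined by an or.

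The Introduction describes DED as "characterized by a loss of homeostasis of the tear film, which is accompanied by ocular symptoms", and gives the aim as finding out whether the combined treatment "leads to an improvement of symptoms and signs in patients with DED due to MGD". Section 2.3 states that "DED symptoms were assessed with the ocular surface disease index (OSDI) and symptom assessment in dry eye (SANDE) questionnaires". Section 2.6 sizes the study on F-NIBUT and MGYSS: "It was calculated on the basis of assumed mean differences in F-NIBUT and MGYSS between the treatment and control groups at 2 months", at 3.04 ± 3.86 and 19.75 ± 5.45, giving 26 eyes per group. Section 2 describes the study as non-randomised and unmasked, run from April 2022 to January 2023.

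**The concern.** The Introduction joins two things, a tear-film disturbance and symptoms. Criterion 2 contains one symptom item and two sign items and, as written, is met by any one of them. A patient with OSDI 4 and NIBUT 9 s satisfies it. So does a patient with OSDI 14, NIBUT 15 s and no staining. The exclusions set no symptom or tear-film threshold, criterion 3 adds only lid and gland findings, and Section 2.6 defines no subset, so nothing else in the document supplies the missing half.

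The conclusion will be stated for symptoms and signs in patients with DED. Patients below the OSDI threshold can show only a limited fall in OSDI, and change in OSDI is also a dependent variable in the planned stepwise regression. Patients entered on OSDI alone start with neither short NIBUT nor qualifying staining, and may have less to gain on F-NIBUT, the outcome that determines the sample size. With non-randomised groups, the mix of entry routes may also differ between arms.

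**Working it through.** **1. The plan's own figure.** Inputs from Section 2.6: F-NIBUT difference 3.04, SD 3.86; MGYSS difference 19.75, SD 5.45; significance level 0.05 (taken as two-sided); power 80%.

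n per group = 2 × [(1.960 + 0.842) × SD / difference]²

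- F-NIBUT: 2 × (2.802 × 3.86 / 3.04)² = 25.3, rounded up to 26. Normal-approximation power at 26 is 81.0%; the t-test gives 79.5%.
- MGYSS: 2 × (2.802 × 5.45 / 19.75)² = 1.2, rounded up to 2.

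The stated 26 is reproduced, and F-NIBUT drives it. The entry rule does not appear in the formula, so the stated N does not change.

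**2. Who the written rule admits.** Each item is met (1) or not met (0). Criterion 3 applies to every row.

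| OSDI ≥ 13 | NIBUT < 10 s | Staining | Any one item | Symptom plus a sign item |
|---|---|---|---|---|
| 0 | 0 | 0 | no | no |
| 1 | 0 | 0 | **yes** | no |
| 0 | 1 | 0 | **yes** | no |
| 0 | 0 | 1 | **yes** | no |
| 0 | 1 | 1 | **yes** | no |
| 1 | 1 | 0 | yes | yes |
| 1 | 0 | 1 | yes | yes |
| 1 | 1 | 1 | yes | yes |

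The written rule accepts 7 of 8 patterns, and symptom plus sign accepts 3. The difference is 4: three with OSDI below 13 and one with OSDI of at least 13 but no qualifying tear-film or staining item. These are counts of patterns, not shares of patients.

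**3. Room to improve on OSDI.** A patient entered with item 2.1 not met has OSDI below 13, so the largest possible fall is below 13 points. SANDE has no entry threshold, so no such limit follows for it.

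**4. Illustration for F-NIBUT.** Assume that a share q of eyes gains nothing extra on F-NIBUT, that the SD stays at 3.86, and that there are 26 independent eyes per group. The expected difference is 3.04 × (1 − q). Power is for the two-sided t-test.

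| q | Expected difference (s) | Power |
|---|---|---|
| 0 | 3.04 | 79.5% |
| 10% | 2.74 | 71% |
| 20% | 2.43 | 61% |
| 30% | 2.13 | 50% |

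The document does not give q. If the pilot (16 eyes of 8 patients per group) recruited under the same rule, some of this dilution is already inside 3.04.

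**The case against.** The strongest reply has five parts.

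- **No patient is free of signs.** Criterion 3 is cumulative with criterion 2, and all five of its findings are lid or gland signs. This stands. A reader might infer that sign-free patients can enter, but they cannot. The gap concerns tear-film and staining signs only. MGYSS, MGYCS, MGYLS, gland loss and MGD grade remain assessable in everyone.
- **OSDI below 13 is not absence of symptoms.** This also stands. A reader might infer that the rule admits symptom-free patients by design, but it admits patients below a threshold on one questionnaire.
- **The objective is not contradicted.** The aim does not require each patient to exceed a threshold on both symptoms and signs. This is right: the aim is diluted, and the conflict is with the Introduction's description of DED. That description is introductory rather than an eligibility rule, but it is the only account of the disease the document gives.
- **The intended rule is uncertain.** The list asks for one item yet ends in an and, whereas the MGD list ends in an or. The governing phrase is a diagnosis according to a cited report, which cannot be consulted here. This lowers confidence that the loose rule was the one applied. It does not remove the need for correction, because this sentence defines the study population.
- **The power figures are hypothetical.** The shares are assumed, nothing in the document sets a ceiling on NIBUT, and the pilot may already contain such eyes. This stands, so the figures show direction and scale only.

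A possible imbalance in entry route between groups is one instance of a general consequence of non-randomised allocation, not something peculiar to this criterion. Section 2.1 does say that some broad criteria are meant to reflect the patient population, but it says so of comorbidity, prior treatment and surgery, not of the DED criterion.

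**Conclusion.** The point holds in a limited form. Taken as written, criterion 2 admits patients with OSDI below 13, and patients with OSDI of at least 13 but neither short NIBUT nor qualifying staining. Neither group matches the Introduction's description of DED as a tear-film disturbance accompanied by symptoms, and no other section closes the gap. The certain effect is the cap of less than 13 points on OSDI improvement for the first group. The effect on F-NIBUT is plausible but cannot be sized, because the number of such patients is not reported.

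A reader might infer that the study is underpowered for this reason. The document does not support that: 26 eyes per group follows from the stated inputs, and the pilot may already reflect the same mix. The conclusion assumes that the words asking for one condition were applied literally; the stray and leaves that open. It should be corrected, but it does not invalidate the gland outcomes.

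**What to change.** **Criterion 2.** Reconcile it with the Introduction and with its own wording by requiring the symptom item plus at least one of the two sign items. State whether first or average NIBUT counts, and whether the sign must be present in the analysed eye, since OSDI is recorded per subject and signs per eye. State also which rule was actually applied.

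**Patients already enrolled.** Section 2 gives the study period as April 2022 to January 2023, so this may be the only part that can still be acted on. If any one item sufficed, report the number of patients and eyes by entry route and group. Show the between-group differences in those meeting both halves beside the full result, and limit the conclusion about symptoms and signs in patients with DED to what that subset supports.

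**Cost.** One line in Section 2.1 and one table, largely from baseline data. There are two drawbacks.

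- The subset is smaller and excludes eyes with short NIBUT whose owners score below 13 on OSDI, although these eyes may have full room on F-NIBUT. If 21 of 26 eyes per group remained (an assumed figure), t-test power for 3.04 ± 3.86 would be about 70%, so the subset should be read by its estimate and confidence interval rather than its p-value.
- Staining outcomes use the Oxford scale (Section 2.3.4) while entry uses stain counts, so flagging patients retrospectively needs the screening counts.

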### **2.2 Experimental design**

A flowchart showing the experimental design of the study is presented in Fig.1. Patients with MGD were classified into the treatment and control groups. All patients received a home-based therapy based on Therapearl eye mask warming compress (Bausch & Lomb, Madrid, Spain) twice a day and Eystil synfo

eyedrops (Sifi Iberica SL, Madrid, Spain) 4 times a day during the study including the follow-up period. Treatment group patients also underwent a series of three combined treatment sessions of MBE, IPL and MGX at 2-week intervals. All patients underwent a 2-months follow-up from baseline.

### **2.3 Clinical assessment**

Parameters were assessed with the S390L Firefly WDR slit lamp (Shangai Mediworks Precision Instruments Co. Shangai, China) that includes a dry eye module designed to perform objective and non-invasive measures, which are analyzed by an artificial intelligence (AI) identification system (Mediview R3.0 software). To assess treatment efficacy, parameters were measured at baseline and the last visit. DED symptoms were assessed with the ocular surface disease index (OSDI) and symptom assessment in dry eye (SANDE) questionnaires. Ocular surface measurement was carried out by one examiner ([name]) in the following sequence to best preserve the integrity of the tear film to avoid affecting the test results: (1) tear film stability and volume; (2) ocular hyperemia; (3) ocular surface staining (OSS) and (4) meibomian gland analysis. Except for OSDI and SANDE questionnaires, which were collected per subject, all other clinical outcomes were collected per eye. To evaluate treatment safety, post-treatment adverse events were reported.

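### The study is sized in eyes with no rule for a patient's two eyes; if both enter the named tests, a nominal 5% group comparison runs at about 6–16% (assumed inter-eye correlation 0.1–0.9)

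*Combined protocol and SAP*

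**What the plan says.** Section 2.2 places patients in the treatment or control group, so both eyes of a patient always share a group. Under Section 2.4, MBE and MGX are carried out on both eyes, and under Section 2.3.4 staining is done on the right and then the left. Section 2.3 fixes the level of recording: "Except for OSDI and SANDE questionnaires, which were collected per subject, all other clinical outcomes were collected per eye". Sections 2.3.1 to 2.3.5 list 17 such outcomes: 5 for the tear film, 4 for hyperemia, 1 for staining and 7 for the meibomian glands. OSDI and SANDE bring the total to 19.

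Section 2.6 bases the sample size on "assumed mean differences in F-NIBUT and MGYSS between the treatment and control groups", with 3.04 ± 3.86 for F-NIBUT and 19.75 ± 5.45 for MGYSS, "based on the findings of a pilot study with 16 eyes of 8 patients in each group". It concludes that "a sample size of 26 eyes per group would yield a power > 80" per cent, and adds "a statistically significant paired difference of 95% confidence". It gives no number of patients.

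The analyses named are:

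- paired t or Wilcoxon tests within groups;
- unpaired t or Mann-Whitney tests between groups ("Inter-group clinical outcomes, were analyzed with the unpaired");
- Pearson or Spearman correlations;
- a regression for symptoms ("Stepwise multiple linear regression analysis was performed to detect the influential factors in dry eye symptoms");
- a comparison of change in MGYSS by baseline L-MGD grade ("One-Way ANOVA (parametric) was performed to determine if there were statistically significant differences").

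No section mentions a patient mean, a choice of one eye, a mixed model, GEE or an inter-eye correlation.

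**The concern.** Two eyes of one person tend to resemble each other, and here they also share the same group. Each named test treats its rows as independent. If both eyes are entered, a group mean has a variance (1 + ICC) times what the test assumes. P-values are then too small and confidence intervals too narrow for all 17 per-eye outcomes, and the stated power is not delivered.

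The regressions raise a related problem. OSDI and SANDE exist once per patient while the ocular measurements exist once per eye, and Section 2.6 does not say whether the score is repeated for each eye.

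The sample size wording adds doubt, because the inputs are differences between groups but the conclusion speaks of a paired difference. The same text can mean 13 or 26 patients per group.

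**Working it through.** **1. The plan's own figure.** Inputs from Section 2.6: difference 3.04, SD 3.86, 95% confidence (taken as two-sided), power 80%.

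- Two independent samples: 2 × (1.960 + 0.842)² × (3.86/3.04)² = 25.31, so 26 per group. This reproduces the stated number, with every eye counted as independent.
- One-sample (paired) form: half of that, 12.65, so 13. Since 13 patients × 2 eyes is also 26 eyes, the paired wording cannot be dismissed outright. The two-sample form fits the between-group inputs.
- MGYSS by the two-sample formula needs only 2 per group, so F-NIBUT drives the size.
- Slack: 26/25.31 = 1.027. By this formula, any ICC above about 0.03 takes F-NIBUT below 80%.

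**2. Assumptions not in the documents.** 13 patients × 2 eyes per group; 3.86 is the per-eye SD; ICC from 0.1 to 0.9. The relevant ICC is that of the quantity tested, mainly the change from baseline.

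**3. True error at nominal 5%, both eyes entered as rows.** Closed form: 2 × [1 − Φ(1.96/√(1 + ICC))]. The other rows are simulations with no true effect.

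| ICC | 0.1 | 0.2 | 0.3 | 0.5 | 0.7 | 0.9 |
|---|---|---|---|---|---|---|
| Closed form, % | 6.2 | 7.4 | 8.6 | 11.0 | 13.3 | 15.5 |
| Between-group t-test, % | 6.2 | 7.4 | 8.7 | 11.2 | 13.9 | 16.5 |
| Mann-Whitney, % | 5.8 | 7.2 | 8.3 | 10.5 | 12.8 | 15.8 |
| Within-group paired t-test, % | 6.1 | 7.3 | 8.5 | 11.2 | 13.8 | 16.6 |

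The t-test on patient means holds about 5% throughout.

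**4. Valid power for F-NIBUT, 13 patients per group.** The mean of two eyes has variance 3.86² × (1 + ICC)/2. With 3.04/3.86 = 0.7876, normal-approximation power is Φ(0.7876 × √(13/(1 + ICC)) − 1.96). The t-test rows use the noncentral t distribution (24 degrees of freedom at 13 patients per group).

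| ICC | 0.1 | 0.2 | 0.3 | 0.5 | 0.7 | 0.9 |
|---|---|---|---|---|---|---|
| Normal approximation, % | 77 | 74 | 70 | 64 | 59 | 54 |
| Patient-mean t-test, % | 74 | 70 | 67 | 60 | 55 | 51 |
| Patients per group for 80% (t-test) | 15 | 17 | 18 | 20 | 23 | 26 |

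For MGYSS the expected test statistic is (19.75/5.45) × √(13/2) = 9.24 even at ICC 1, so its power is not at risk.

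**5. Symptom regressions.** With one eye-level predictor and 13 patients, repeating the score for both eyes gives an error of 6.3% to 17.5% over the same ICC range. One row per patient gives about 5%.

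No single figure is claimed for the correlations or the ANOVA, because they depend on further assumptions.

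**The case against.** The plan never says that both eyes enter as separate rows. Bilateral treatment and examination show what was done, not what was analysed. If one eye per patient was meant, the error is 5% and 26 eyes are 26 patients. This stands as a limit on the finding: the inflation is conditional. The eye-based size and the two-eye pilot make the bilateral reading the likelier one, and the missing rule has to be supplied on either reading.

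The ICC has no anchor in the documents, and the correlation of change scores may differ from that of raw values. That also stands. At 0.1 the inflation is small, and nothing here favours the upper end over the lower.

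The power comparison can mix methods. By t-test, 26 fully independent eyes per group already give 79.5%, and 13 patient means at ICC 0 give 77.8%. Part of the fall to 74–51% therefore comes from the t distribution and fewer degrees of freedom. The like-for-like comparison is the normal approximation, 81% falling to 77–54%, which still misses the stated power at every ICC shown.

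The 26 is a planned number. The flowchart, which might show actual counts, is not reproduced in the text available, so 13 patients per group remains an assumption.

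Finally, stepwise selection is a weakness in its own right. It matters here because the number of independent rows for it depends on the fellow-eye rule.

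**Conclusion.** The concern holds. Section 2.6 counts eyes, names tests for independent observations and leaves the fellow-eye rule unstated. Followed on its likelier reading, with 13 patients contributing two eyes each, it gives a true between-group error of about 6% to 16% in place of 5%. F-NIBUT power is then 77–54% (normal approximation) or 74–51% (t-test), against more than 80% stated. Both ranges rest on an assumed ICC of 0.1 to 0.9, and the power figures also on 3.86 being the per-eye SD.

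All 17 per-eye outcomes are affected. MGYSS power is safe, and group comparisons of OSDI and SANDE are unaffected if each patient is counted once. On the one-eye reading there is no inflation, but the plan would have to say so.

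**What to change.** In Section 2.6, state the unit of inference and the fellow-eye rule:

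1. **Continuous per-eye outcomes, within and between groups:** analyse the mean of the patient's two eyes with the tests already named.
2. **LLG, U- and L-MGD grades and the Oxford staining grade:** use Mann-Whitney or Wilcoxon on the two-eye mean grade. In simulation of a four-level grade, Mann-Whitney on this mean held 4.8–5.1%. The alternative is an ordinal model clustered on patient with a small-sample correction.
3. **Correlations, and change in MGYSS by baseline L-MGD grade with its Bonferroni pairs:** use a random patient intercept with degrees of freedom based on patients, or a permutation test that moves both eyes of a patient together. Keep the grade at eye level here, because a half-grade belongs to no group. Robust clustered variance alone is not enough at this size: in simulated correlations with 13 patients, the bias-reduced (CR2) form still gave 6.4–7.7%. Block permutation held 4.7–5.3% across the correlations and the ANOVA.
4. **OSDI and SANDE regressions:** one row per patient, with each ocular predictor as the two-eye mean. At 13 patients per group that is 26 rows pooled, or 13 within one group, too few for stepwise choice among up to 17 ocular predictors. With 17 null predictors, at least one passed P < 0.05 at the first step in 50–58% of simulated runs. Name a few candidates in advance or label the result exploratory.
5. **Reporting:** give the numbers of patients and of eyes for every result.
6. **Sample size:** restate it in patients, with the assumed ICC and the power it delivers, and resolve the paired wording.

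No new measurements are needed. Items 1 and 4, and the mean-grade option in item 2, use methods already named. Item 3 and the ordinal option need added modelling or a permutation routine. The price is wider confidence intervals and a lower stated F-NIBUT power. Section 2 dates the conduct from April 2022 to January 2023. If enrolment is closed, the patient numbers in the working serve only as a reference, and what remains is a patient-level reanalysis with a statement of the power actually delivered.
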